4.3. Exclusion Criteria

Subjects who meet *any* of the following exclusion criteria are not to be enrolled in this study.

- 1) Prior treatments for RA as follows:
 - a) Alkylating agents, eg chlorambucil or cyclophosphamide, at any time
 - b) Previous treatment with JAK inhibitor
 - c) Leflunomide use within 8 weeks prior to Day 1 or in the case of cholestyramine washout, within 4 weeks prior to Day 1
 - d) Discontinuation of hydroxychloroquine or chloroquine less than 4 weeks prior to Day 1
 - e) Cyclosporine, other calcineurin inhibitors, gold therapy, sulfasalazine, mycophenolate mofetil, or azathioprine within 4 weeks of Day 1 visit
 - f) Subjects that have failed prior therapy with a bDMARD are not eligible to participate. Subjects with prior exposure to one bDMARD may be enrolled (approximately 20% of total study population) if there is documented evidence of limited exposure (ie, less than 3 months) to the bDMARD
 - g) Any previous use of adalimumab
 - h) Any previous use of rituximab or other selective B lymphocyte depleting agents (including experimental agents)
- 2) Known hypersensitivity or allergy to the study drug(s), its metabolites, or formulation excipients.
- 3) Oral steroids at a dose >10 mg/day of prednisone (or equivalent) or a prescription for oral steroids which has changed within 4 weeks of Day 1.

- 4) Receipt of an intra-articular or parenteral corticosteroid injection within 4 weeks prior to Day 1.
- 5) Use of nonsteroidal anti-inflammatory drugs (NSAIDs) which have not been at a stable dose (defined as no change in prescription) for at least 2 weeks prior to Day 1. NOTE: subjects are permitted to take acetylsalicylic acid at a dose of ≤ 325 mg daily for cardiac prophylaxis, or occasional NSAIDs for non-RA indications (eg, headache).
- 6) Administration of a live/attenuated vaccine within 30 days prior to Day 1, or planned during the study.
- 7) Participation in any clinical study of an investigational drug/device within 4 weeks or 5 half-lives prior to Screening, whichever is longer. Exposure to investigational biologics should be discussed with the Sponsor.
- 8) Have undergone surgical treatments for RA, including synovectomy or arthroplasty in >4 joints
- 9) Have any chronic, uncontrolled medical condition, which would put the subject at increased risk during study participation, such as uncontrolled: diabetes, hypertension, morbid obesity, thyroid, adrenal, pulmonary, hepatic, renal, neurologic or psychiatric disease, or other disease of concern, as per judgment of investigator
- 10) Have a history of major surgery (requiring regional block or general anesthesia) within the last 3 months prior to Screening or planned major surgery during the study.
- 11) Have a moderately to severely active, generalized musculoskeletal disorder that would interfere with assessment of study parameters or increase risk to the subject by participating in the study, eg, generalized osteoarthritis, systemic inflammatory condition other than RA such as, but not limited to: ankylosing spondylitis, reactive arthritis, psoriatic arthritis, inflammatory bowel disease associated arthropathies, systemic lupus erythematosus, scleroderma, inflammatory myopathy, mixed connective tissue disease, overlap syndrome, or gout. Subjects with any history of Felty's syndrome or juvenile idiopathic arthritis are excluded, regardless of the disease activity level at Screening. (NOTE: subjects with concurrent Sjogren's syndrome or limited cutaneous vasculitis associated with RA are not excluded, and may be enrolled, based on investigator judgment).
- 12) Active autoimmune disease other than those listed above, that would interfere with assessment of study parameters or increase risk to the subject by participating in the study, eg, inflammatory bowel disease, uncontrolled thyroiditis, systemic vasculitis, transverse myelitis or uveitis.
- 13) History of or current moderate to severe congestive heart failure (New York Heart Association [NYHA] class III or IV), or within the last 6 months, a cerebrovascular accident, myocardial infarction, unstable angina, unstable arrhythmia, new or significant ECG finding at Screening, or any other cardiovascular condition which, in the opinion of the investigator, would put the subject at risk by participation in the study.

- 14) History of malignancy within the past 5 years prior to Screening (except for adequately treated basal cell carcinoma or non-metastatic squamous cell carcinoma of the skin or cervical carcinoma in situ, with no evidence of recurrence).
- 15) History of lymphoproliferative disease or current lymphoproliferative disease
- 16) History of gastrointestinal perforation.
- 17) History of organ or bone marrow transplant.
- 18) Positive serology for human immunodeficiency virus (HIV) 1 or 2.
- 19) Evidence of active Hepatitis C Virus (HCV) infection. Subjects with positive HCVAb at screening, require reflex testing for HCV RNA. Subjects with positive Hep C RNA viral load (VL) at screening will be excluded. Subjects with positive HCV Ab, but negative HCV RNA VL are eligible per investigator judgment, but require ongoing monitoring as outlined in the schedule of assessments. Subject with active HCV during the study, as evidenced by RNA positivity will be discontinued from study drug as outlined in the protocol.
- 20) Evidence of active Hepatitis B Virus (HBV) infection. Subjects with positive HBV surface antigen (HBsAg) at screening are excluded from the study. Subjects with positive HBV core Ab and negative HBsAg, require reflex testing for HBV DNA. Subjects with positive HBV DNA at screening will be excluded. Subjects with positive HBV core Ab, and negative HBV DNA are eligible per investigator judgment, but may require prophylactic treatment in accordance with HBV treatment guidelines/local standard of care and require ongoing monitoring with blood tests for HBV DNA every 3 months, as outlined in the schedule of assessments. Subject with evidence of active Hepatitis B during the study, as evidenced by DNA positivity, will be discontinued from study drug as outlined in the protocol.
- 21) History of opportunistic infection, or immunodeficiency syndrome, which would put the subject at risk, as per investigator judgment.
- 22) Active infection that is clinically significant, as per judgment of the investigator, or any infection requiring hospitalization or treatment with intravenous anti-infectives within 60 days of Screening; or any infection requiring oral anti-infective therapy within 30 days of Screening.
- 23) Currently on any therapy for chronic infection (such as pneumocystis, cytomegalovirus, herpes zoster, and atypical mycobacteria). Past history of disseminated Staphylococcus aureus or disseminated Herpes simplex infection.
- 24) History of symptomatic herpes zoster infection within 12 weeks prior to Screening or have history of disseminated/complicated herpes zoster infection (multi-dermatomal involvement, ophthalmic zoster, central nervous system involvement or postherpetic neuralgia)
- 25) History of an infected joint prosthesis or other implanted device with retention of the prosthesis or device in situ.

- 26) Current drug, tobacco or alcohol abuse, per investigator judgement.
- 27) Any known condition or contraindication as addressed in the local labeling for adalimumab and/or MTX that would preclude the subject from participating in this study.
- 28) Any condition including active fibromyalgia that based on the investigator's opinion would make it difficult to appropriately assess RA activity for the purposes of this study.
- 29) Any condition or circumstances which in the opinion of the Investigator or Sponsor may make a subject unlikely or unable to complete the study or comply with study procedures and requirements.
- 30) Use of prohibited medication as outlined in section 5.5
- 31) Significant blood loss (>450 mL) or transfusion of any blood product within 12 weeks prior to Day 1.
- 32) Tests performed at the central laboratory at Screening that meet any of the criteria below (out of range lab values may be rechecked one time, after consultation with the sponsor or its designee, before subject is considered a screen-failure):
 - a) Hemoglobin <8.0 g/dL (International System of Units [SI]: <80 g/L);
 - b) White blood cells <3.0 x 10³ cells/mm³ (SI: <3.0 x 10⁹ cells/L);
 - c) Neutrophils <1.5 x 10³ cells/mm³ (SI: <1.5 x 10⁹ cells/L);
 - d) Lymphocytes <0.5 x 10³ cells/mm³ (SI: <0.5 x 10⁹ cells/L);
 - e) Platelets <100 x 10³ cells/mm³ (SI: <100 x 10⁹ cells/L);
 - f) Alanine aminotransferase (ALT) or aspartate aminotransferase (AST) ≥1.5x ULN;
 - g) Total bilirubin level ≥2x ULN unless the subject has been diagnosed with Gilbert's disease and this is clearly documented;
 - h) Estimated creatinine clearance <40 mL/min based on the Cockcroft Gault formula.

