3.2. Study Design

This is a randomized, double-blind, placebo- and active-controlled, Phase 3 study in adult male and female subjects with active RA who have an inadequate response to MTX. The study is designed to evaluate the efficacy, safety and tolerability of filgotinib as well as its effect on patient-reported outcomes, including work productivity, fatigue, and quality of life. In addition, PK will be assessed.

Adult male and female subjects with active RA will be screened to determine eligibility as per the inclusion and exclusion criteria (see Section 4.2 and 4.3, respectively). The Screening period will be up to 28 days. The screening window may be extended to up to 42 days prior to the Day 1 visit for subjects who require repeat collection of radiographs.

Written informed consent must be obtained before any study-related procedures take place. During the Screening period, following signing of the informed consent form (ICF), radiographs (hands, wrists, and feet) will be sent for central review for confirmation of the number of documented joint erosions. Note that radiographs need to be sent for central review as soon as possible after capture and prior to Day 1 to allow for central reading and confirmation of the joint erosions for eligibility purposes.

Subjects will be randomized in a 3:3:2:3 ratio to filgotinib 200 mg, filgotinib 100 mg, active comparator (adalimumab), or matching placebo controls administered for up to 52 weeks in a double blind fashion.

At Week 14, subjects who have not achieved a 20% improvement from Day 1 in both swollen joint count (SJC) and tender joint count (TJC) will discontinue investigational therapy but will continue with study visits and assessments per protocol. All subjects who discontinue from investigational therapy, are to receive standard of care treatment for their RA as determined by the investigator. At Week 24 all subjects assigned to placebo + MTX will be reassigned 1:1 to either filgotinib 100 mg q.d. or 200 mg q.d. in addition to MTX in a blinded fashion and will continue the study through Week 52.

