Female subjects of childbearing potential must agree to use highly effective birth-control methods as outlined in [Appendix 5](#) and must agree to continue their use during the study and for at least 35 days after the last dose of study medication. The use of hormonal contraceptives will be recorded in the Concomitant Therapy section of the eCRF. Applicable procedures and treatment guidance based on package inserts will be followed.

Hormone replacement therapy, thyroid replacement and other chronic therapies (such as those for well-controlled diabetes or hypertension) are permitted during the study, and should be kept at a stable dose and regimen, as much as possible.

Vitamin, mineral or herbal supplementations are permitted during the study per judgment of investigator, and should be kept at a stable dose and regimen, as much as possible.

Prohibited concomitant medications (and their wash out period as applicable) while on study drugs include:

- Any DMARDs, other than background MTX and anti-malarials
- Oral or injectable gold within 4 weeks prior to Day 1
- Sulfasalazine within 4 weeks prior to Day 1
- Azathioprine within 4 weeks prior to Day 1
- D penicillamine within 4 weeks prior to Day 1
- Cyclosporine within 8 weeks prior to Day 1
- Leflunomide within 8 weeks prior to Day 1 or a minimum 4 weeks prior to Day 1 if after 11 days of standard cholestyramine therapy.
- Any cytotoxic agent, including chlorambucil, cyclophosphamide, nitrogen mustard, and other alkylating agents.
- Use of any JAK inhibitor or other small molecule immunomodulator
- Any injectable corticosteroids and receipt of an intra-articular or parenteral corticosteroid injection within 4 weeks prior to Day 1 is prohibited.
- Potent P-gp inducers (e.g. rifampin, phenytoin, carbamazepine, and St. John's wort) within 3 weeks prior to Day 1

Subjects with prior exposure to a TNF α inhibitor (with the exception of adalimumab) or a bDMARD for RA may be enrolled in the study (up to 20% of the enrolled population) if they did not fail previous TNF α inhibitor or bDMARD due to lack of efficacy and if there is documented evidence of limited exposure (less than 3 months).

Previous treatment at any time with a cytotoxic agent, other than MTX is prohibited.

Previous use of JAK inhibitors is prohibited.

Previous treatment with any B-cell depleting agent is prohibited.

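### Exclusion 1e gives cyclosporine a 4-week washout, but Section 5.5, binding through Exclusion 30, requires 8 weeks

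*Protocol*

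**What the plan says.** Three lines of the Protocol bear on cyclosporine before Day 1.

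- Section 4.3, Exclusion 1e, under prior treatments for RA: "Cyclosporine, other calcineurin inhibitors, gold therapy, sulfasalazine, mycophenolate mofetil, or azathioprine within 4 weeks of Day 1 visit".
- Section 5.5, in the list of prohibited medications: "Cyclosporine within 8 weeks prior to Day 1". The lead-in to that list reads "Prohibited concomitant medications (and their wash out period as applicable) while on study drugs include", so it covers washout intervals as well as use during treatment.
- Section 4.3, Exclusion 30: "Use of prohibited medication as outlined in section 5.5".

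Section 4.3 opens by saying that a subject who meets any of the exclusions is not to be enrolled. On timing, Section 3.2 says "The Screening period will be up to 28 days" and, for subjects who need repeat radiographs, "The screening window may be extended to up to 42 days prior to the Day 1 visit".

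**The concern.** One drug, counted back from the same day, has two washout intervals in current operative text. The shorter one sits where a site looks first: 1e is the only line in Section 4.3 that names cyclosporine. Exclusion 30 names no drug and gives no interval. A coordinator checking a cyclosporine history against Section 4.3 finds a specific and apparently complete answer in 1e, with nothing to suggest that a longer interval applies elsewhere.

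If the site acts on 1e, a subject could be randomized inside an immunosuppressant washout that the Protocol itself requires. Under the 3:3:2:3 allocation, 3 + 3 + 2 = 8 of every 11 subjects start filgotinib or adalimumab on top of methotrexate on Day 1. Section 1.5 discusses serious infection as a risk for both drugs. The enrolment would also breach Exclusion 30 and would be reported as such, because SAP Section 4.3 counts and lists subjects who fail specific eligibility criteria.

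**Working it through.** No power, alpha or sample-size figure is involved. The check compares the texts and converts weeks to days.

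**Does Section 5.5 bind at eligibility?** Exclusion 30 refers to it directly. It could be argued that Exclusion 30 reaches only current use, since the Section 5.5 lead-in speaks of concomitant medication. But the lead-in expressly includes washout periods, and the cyclosporine line is itself a window before Day 1. Read that way, it is an eligibility rule.

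**Size of the gap.**

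- Exclusion 1e: 4 weeks × 7 = 28 days before Day 1.
- Section 5.5: 8 weeks × 7 = 56 days before Day 1.
- Difference: 56 − 28 = 28 days.

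**Who is affected.**

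| Last cyclosporine dose before Day 1 | Exclusion 1e | Exclusion 30 with Section 5.5 | Eligible? |
|---|---|---|---|
| Up to 28 days | barred | barred | No |
| More than 28 and up to 56 days | passes | barred | No, but 1e suggests yes |
| More than 56 days | passes | passes | Yes, on this point |

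**Is the difference deliberate?** These are the DMARDs with an interval in both sections:

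| Drug | Section 4.3 | Section 5.5 | Agree? |
|---|---|---|---|
| Gold | 4 weeks (1e) | 4 weeks | Yes |
| Sulfasalazine | 4 weeks (1e) | 4 weeks | Yes |
| Azathioprine | 4 weeks (1e) | 4 weeks | Yes |
| Leflunomide | 8 weeks, or 4 after cholestyramine (1c) | 8 weeks, or 4 after cholestyramine | Yes |
| Cyclosporine | 4 weeks (1e) | 8 weeks | **No** |

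Four of five agree. For example, azathioprine in Section 5.5 reads "Azathioprine within 4 weeks prior to Day 1", as in 1e, and leflunomide in 1c reads "Leflunomide use within 8 weeks prior to Day 1", as in Section 5.5. Nothing in the documents explains two cyclosporine intervals.

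**What it means for timing a screening visit.** The last dose must precede the start of screening by the washout minus the length of the screening window:

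- 1e, 28-day window: 28 − 28 = 0 days. A subject who stops on the first day of a full window is at the 1e limit on Day 1.
- 1e, 42-day extension: 28 − 42 = −14, so the 28 days are already complete before Day 1.
- Section 5.5, 28-day window: 56 − 28 = 28 days.
- Section 5.5, 42-day extension: 56 − 42 = 14 days.

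Under 1e the washout can be completed within screening. Under Section 5.5 it cannot be, in either window. The two lines therefore give a site different instructions on when to stop the drug and when to screen.

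**The case against.** The strongest reply is that the Protocol already resolves the conflict. Exclusions are cumulative, both lines can be applied together, and the stricter one governs. An exclusion says who is barred; it does not confer eligibility. On this view 1e is merely redundant for cyclosporine, and an error needs a site to ignore Exclusion 30. This is right about which rule binds. It does not remove the risk, because the line that names the drug gives the shorter interval and the line that governs names neither drug nor interval.

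Other points stand in part:

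- The documents give no pharmacokinetic or clinical reason to prefer 8 weeks to 4, and do not say which was intended. Clinical harm is therefore not shown. What is shown is that the binding text and the visible text disagree.
- The two lists differ elsewhere. Exclusion 1e gives 4 weeks to mycophenolate and to other calcineurin inhibitors, for which Section 5.5 sets no interval. Section 5.5 gives 4 weeks to D-penicillamine, which Section 4.3 does not name. These are omissions from one list, not contradictory numbers.
- Nothing requires a washout to fit inside screening, and leflunomide without cholestyramine also needs 8 weeks. The screening arithmetic illustrates the practical difference; it is not separate evidence of error.
- Prior RA medications are recorded in the eCRF (Section 5.5), and monitors verify source data (Section 9.1.6). A breach would probably be found, but possibly only after the subject had been dosed.

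**Conclusion.** The concern holds. Exclusion 1e understates the binding cyclosporine washout by 28 days, and candidates whose last dose was more than 28 and up to 56 days before Day 1 get conflicting answers from Section 4.3. This rests on reading Exclusion 30 as importing the washout intervals in Section 5.5, which is the natural reading of that list's lead-in.

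The practical effect is modest. The number of such candidates is not given and is likely small, and no effect on power, type I error or the per-protocol set is claimed. It should still be corrected, because it is operative eligibility text and a site relying on 1e could enrol a barred subject.

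**What to change.** Take cyclosporine out of the 4-week list in Exclusion 1e and give it its own 8-week exclusion before Day 1, matching Section 5.5. The other drugs in 1e can stay at 4 weeks, since Section 5.5 either agrees with that interval or sets none. If the sponsor intended 4 weeks, change the Section 5.5 cyclosporine line instead. In either case, bring any eligibility checklist used by sites to the same interval.

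The cost is a one-line protocol clarification and a checklist update. With 8 weeks, a few candidates would be deferred by up to 4 weeks; Section 6.2.1 already allows one rescreening in consultation with the sponsor or its designee. No analysis changes.

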Blood samples for biomarker analysis should be collected at Day 1, Weeks 4, 8, 12, 24, 36, and Week 52 or ET and urine samples should be collected at Day 1, Weeks 12, 24, and Week 52 or ET.

Radiographs of the bilateral hands, wrists, and feet should be taken at Screening, Weeks 12, 24, and Week 52 or ET. However, if a subject prematurely discontinues study participation and has had X-rays performed within the previous 12 weeks, then X-rays do not need to be repeated at the ET visit. Radiographs after enrollment may be done +/- 7 days of the scheduled visit. Post treatment follow-up assessments include AEs, concomitant medications, physical examination, 12-lead ECG, weight, vital signs, blood and urine sampling for safety laboratory tests, and urine pregnancy tests (females of child bearing potential only).

CCI

CCI

Test Product, Dose, and Mode of Administration:

200 mg filgotinib orally q.d.
100 mg filgotinib orally q.d.

Reference Therapy, Dose, and Mode of Administration:

Adalimumab injection (40 mg s.c.) or PTM s.c. q2w
PTM filgotinib 200 mg orally q.d.
PTM filgotinib 100 mg orally q.d.

Required Background Medication:

Stable prescription of weekly MTX as described in the inclusion criteria and administered according to the local product label/standard of care.

Criteria for Evaluation:

Safety:

Safety will be assessed by documentation of AEs, clinical laboratory tests, physical examinations, vital signs, and 12-lead ECGs during the study.

Efficacy: The primary endpoint is the proportion of subjects who achieve an ACR20 response at Week 12.

The key secondary endpoints are:

- The proportion of subjects who achieve DAS28 (CRP) \leq 3.2 at Week 12
- Change from Baseline in the HAQ-DI score at Week 12
- The proportion of subjects who achieve DAS28 (CRP) $<$ 2.6 at Week 24
- Change from Baseline in mTSS at Week 24

Pharmacokinetics: Plasma concentrations of filgotinib and its metabolite (GS-829845) will be analyzed.

Statistical Methods: The primary analysis set for efficacy analyses will be the Full Analysis Set (FAS), which includes all randomized subjects who received at least one dose of study drug.

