3.4. Duration of Treatment

Subjects are planned to participate in the study for approximately 60 weeks (from Screening visit to Follow-up visit or entry into the LTE); the duration of dosing is up to 52 weeks.

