Biomarker Blood Samples: Plasma biomarker, serum biomarker, transcriptome, TCR/BCR repertoire ^p		X		X	X	X					X			X		X	
vfPBMC & Leukocyte subsets ^q		X		X	X	X					X			X		X	
Serology ^r	X																
Viral Monitoring ^s						X					X			X		X	
CCI																	

EVENT		Screening ^a	Treatment Period													Follow Up ^d	
			Day 1 ^b	W2	W4	W8	W12	W14	W16	W20	W24	W26	W30	W36	W44	W52/ ET ^c	Post Treatment Week 4
Visits	Visit window (Days)		(±3 days)	(±3 days)	(±3 days)	(±3 days)	(±3 days)	(±3 days)	(±3 days)	(±3 days)	(±3 days)	(±3 days)	(±3 days)	(±7 days)	(±7 days)	(±7 days)	(±7 days)
Imaging	Hand, wrist and feet radiographs ^h	X				X				X					X		
	CCI CCI																
Assessment of Adverse Events		X	X	X	X	X	X	X	X	X	X	X	X	X	X	X	
Concomitant medications		X	X	X	X	X	X	X	X	X	X	X	X	X	X	X	
Randomization/reassignment			X ^x				X ^y			X ^z			X ^{aa}	X ^{aa}	X ^{aa}		
Study Drug(s) Dispensation ^{bb}			X		X	X	X		X	X	X		X	X	X		
Self-injection (or caregiver) training ^{cc}			X														
Review entry criteria for LTE (if applicable)															X		

- a Screening window is 28 days prior to Day 1, the window may be extended to up to 42 days prior to the Day 1 visit for subjects who require repeat collection of radiographs
- b Subject will begin medication on Day 1, following baseline assessments and randomization.
- c Early Termination Visit to be performed if subject discontinues before Week 52
- d The follow-up visit will be performed only for subjects discontinuing prematurely from the study and for those completing Week 52, but not entering the LTE.
- e Eligibility criteria check based on the laboratory results from the Screening visit, TJC/SJC at screening and Day 1 and for female subjects of childbearing potential, the urine pregnancy test at Day 1.
- f Medical History includes smoking status, average weekly alcohol consumption, family history of coronary heart disease (CHD) any other chronic medical conditions or prior surgeries
- g At Screening, Week 24, and Week 52 (or at ET), a complete physical examination should be performed. Symptom-directed exams should be performed at all other visits. Height will be measured at Screening only.
- h Chest X-ray should be performed unless performed in the previous 3 months, and results are available at the site.

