- i Subject reported outcomes are recommended to be performed at the beginning of each visit prior to any other visit-related procedures (other than signing of informed consent). Subject reported outcomes should be performed where available
- j Vital signs are defined as heart rate, respiratory rate, blood pressure (systolic and diastolic) and body temperature.
- k For female subjects of childbearing potential only. To be performed on a serum sample at Screening and on urine samples for other visits. For female subjects entering the LTE, at the Week 52 visit pregnancy test should be performed on serum. During the periods where visits are every 6-8 weeks, women should continue to have pregnancy tests every 4 weeks, using home pregnancy urine tests, that will be provided to them. The site will call the subject every 4 weeks to obtain results of these pregnancy tests and will record the information in the source documents and CRF. If any pregnancy test is positive, study drug should be immediately interrupted and should come to the site for serum pregnancy test.
- l Refer to list provided in Laboratory assessment table ([Appendix 6](#)).
- m Urine for biomarkers is to be collected at Day 1 and Weeks 12, 24, 52 and ET (if applicable)
- n **CCI**
- o The PK sample at Week 4 should be collected at least 30 minutes post study drug dose in the clinic. PK samples at Week 12 and Week 24 should be collected prior to study drug dose (within 2 hours prior to dosing). The PK sample at Week 52 or ET can be collected at anytime during the visit.
CCI
- p Details of biomarker collection are outlined in lab manual
- q For sites within US and Canada only
- r Hepatitis B surface Ag and core Ab, reflex Hep B DNA, Hepatitis C Ab, reflex HCV RNA, HIV 1 and 2 at Screening.
- s Viral monitoring for HBV or HCV as applicable (see Exclusion criteria, Section 4.3)
- t At sites participating in carotid artery ultrasounds only. The following blood samples should be drawn in a fasting state; HbA1c, Leptin, LDL particle, Homocystein, Apo A1/B
- u Radiographs performed after enrollment may be done ± 7 days of the scheduled visit. If subject discontinues study early and has had X-rays <12 weeks prior to the ET visit, X-rays do not need to be repeated at the ET visit
- v **CCI**
- w **CCI**
- x Upon qualification for the study

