4.2.1. Duration of Exposure to Study Drug

Total duration of exposure to any study drug will be defined as $(\text{last dose date of any study drug} - \text{first dose date of any study drug} + 1)$, regardless of any temporary interruptions in study drug administration and will be expressed in weeks using up to 1 decimal place (eg, 4.5 weeks).

For subjects with a partial last dosing date (ie, month and year of last dose are known), the latest of the dispensing dates of study drug bottles, study drug start dates and end dates, and the imputed last dose date [day imputed as 15] will be used as the final imputed last dose date. If the subject died and the death date is complete (ie, not partial date) and before the imputed last dose date, the complete death date will be used as the imputed last dose date.

If only year is recorded (ie, month and day of last dose are missing), the latest of the dispensing month of study drug bottles, study drug start month, and study drug end month will be used to impute the unknown last dose month. If the subject died and the death date has month and year available and before the imputed last dose month, then the month of death will be used instead. With the month imputed, the aforementioned method will be used to impute the last dose date.

If subjects are continuing on study drug at Week 24 analysis, the earliest of the date of death or data cutoff date for analysis will be used to impute the last dosing date for the calculation of duration of exposure to study drug.

The total duration of exposure to any study drug will be summarized using descriptive statistics and using the number (ie, cumulative counts) and percentage of subjects exposed through the following time periods: Baseline (Day 1), Week 2 (Day 15), Week 4 (Day 29), Week 8 (Day 57), Week 12 (Day 85), Week 14 (Day 99), Week 16 (Day 113), Week 20 (Day 141), Week 24 (Day 169), Week 26 (Day 183), Week 30 (Day 211), Week 36 (Day 253), Week 44 (Day 309) and Week 52 (Day 365). A 7-day window is applied to the last planned on-treatment visit to match the protocol-specified visit window

Summaries will be provided by treatment group for the Safety Analysis Set. No formal statistical testing is planned.

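### HBV DNA testing is required every 3 months, but the schedule leaves 16 weeks between the Week 36 and Week 52 tests

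*Protocol*

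**What the plan says.** Protocol Section 4.3, criterion 20, makes core-antibody-positive, HBV DNA-negative subjects eligible at the investigator's judgment. They may need prophylaxis, and they "require ongoing monitoring with blood tests for HBV DNA every 3 months, as outlined in the schedule of assessments". Criterion 19 sends HCV-antibody-positive, RNA-negative subjects to the same schedule but names no interval, so the 3 months was written for HBV specifically.

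In Appendix 2 the row "Viral Monitoring" carries four marks. Its footnote (s) refers the reader back to Section 4.3 and adds no time points. The entry test is at Screening: footnote r lists "Hepatitis B surface Ag and core Ab, reflex Hep B DNA, Hepatitis C Ab, reflex HCV RNA, HIV 1 and 2 at Screening". Footnote a says "Screening window is 28 days prior to Day 1, the window may be extended to up to 42 days" when radiographs must be repeated. The visit lists in Sections 6.4 and 6.5 name no HBV DNA test.

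Section 3.5.2 makes HBV DNA positivity a reason for permanent discontinuation of study drug. Section 3.4 says "the duration of dosing is up to 52 weeks".

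**The concern.** The criterion sets an interval and says the schedule implements it. The schedule then has no viral test at Week 44, the only planned visit between Weeks 36 and 52. A site that follows the table breaks the criterion, and a site that follows the criterion must order a test that the table does not show. The footnote does not settle this, because criterion and table each refer to the other.

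The DNA test is the trigger for a stopping rule in subjects who were enrolled on condition of being monitored. If reactivation begins soon after a negative Week 36 test, the next scheduled look comes when dosing in this study is ending. Placebo subjects reassigned to filgotinib at Week 24 have Week 36 as their only scheduled test between the switch and Week 52. The protocol does bridge the wider late visit spacing for pregnancy testing, with home tests and calls every 4 weeks, but has nothing similar for HBV.

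**Working it through.** **Inputs**

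- Required interval: 3 months (criterion 20), taken as 89 to 92 calendar days.
- Study days (SAP Section 4.2.1): Week 12 = 85, Week 24 = 169, Week 36 = 253, Week 44 = 309, Week 52 = 365.
- Visit windows (Appendix 2): ±3 days through Week 30; ±7 days at Weeks 36, 44 and 52.
- Dosing: 52 × 7 = 364 days.

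**Step 1: which weeks are marked.** The extracted table is offset, so the row has to be aligned with rows whose visits are given in text. Counting the row label as column 0:

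| Row | Mark columns | Visits stated in text |
|---|---|---|
| Biomarker blood | 2, 4, 5, 6, 11, 14, 16 | Day 1, Weeks 4, 8, 12, 24, 36, 52/ET (Synopsis; Section 6.4) |
| PK | 4, 6, 11, 16 | Weeks 4, 12, 24, 52/ET (Section 6.8) |
| Viral monitoring | 6, 11, 14, 16 | none |

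The Synopsis wording for the first row is "Blood samples for biomarker analysis should be collected at Day 1, Weeks 4, 8, 12, 24, 36, and Week 52 or ET". Both anchor rows show the same offset, so columns 6, 11, 14 and 16 are Weeks 12, 24, 36 and 52/ET. Reading the header literally would not rescue the plan: Weeks 12, 26 and 44 are 98 and 126 days apart.

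**Step 2: gaps.** Gap = later day − earlier day; range = gap ± the sum of the two windows.

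| Interval | Nominal days | In-window range |
|---|---|---|
| Week 12 to 24 | 169 − 85 = 84 | 78 to 90 |
| Week 24 to 36 | 253 − 169 = 84 | 74 to 94 |
| Week 36 to 52 | 365 − 253 = 112 | 98 to 126 |

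The plan's own figure of 3 months is reproduced nominally for the first two intervals and not for the last.

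**Step 3: excess in the last interval.** Nominally 112 − 92 = 20 to 112 − 89 = 23 days. Across the windows the smallest excess is 98 − 92 = 6 days and the largest is 126 − 89 = 37 days. It is never zero.

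**Step 4: exposure without a scheduled test before the end of dosing.** 112 / 364 = 30.8%. For placebo subjects switched at Week 24, filgotinib dosing is 28 × 7 = 196 days, and 112 / 196 = 57%.

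**Step 5: Screening to Week 12.** Week 12 is 84 days after Day 1, and no HBV DNA test is marked on Day 1. The first gap can be 28 + 84 = 112 days, or 42 + 84 = 126 with extended screening (115 and 129 at the late edge of the Week 12 window). It passes 92 days once Screening is more than 92 − 84 = 8 days before Day 1.

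**Step 6: with a Week 44 test.** 309 − 253 = 56 and 365 − 309 = 56 days, each 42 to 70 with windows.

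**The case against.** The best defence is that the schedule is how the 3 months is put into practice: four tests in 364 days average 364 / 4 = 91 days, which is quarterly testing fitted to existing visits. But an average does not describe the spacing. A 16-week gap is not testing every 3 months, and the shortest permitted gap still exceeds the interval.

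A second point is that the footnote sends sites back to the 3-month text and Section 6.7.4 allows additional tests, so a careful site could add the assay at Week 44. That is true, but it leaves compliance with a condition of enrolment to each site.

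Third, the 31% overstates the departure from the rule. This has force. Measured against a strict 3-monthly test, the shortfall is one test about three weeks late. Any schedule whose last test is at the end of dosing leaves a tail; after the proposed fix the tail is still 56 of 364 days (15%).

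Fourth, the Screening-to-Week 12 interval includes up to 42 days before any study drug. That also has force, so it is a side observation here and not the main finding.

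Finally, there is real mitigation. ALT and AST are drawn at every visit including Week 44, confirmed elevations prompt discussion of hepatitis testing (Section 3.5.2), and prophylaxis may be given. These detect liver injury or rest on judgment; none schedules a DNA test.

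**Conclusion.** The concern holds. Criterion 20 and Appendix 2 disagree for the last 16 weeks of dosing. The Week 36 to Week 52 gap is 112 days (98 to 126), which is 20 to 23 days over 3 months nominally and 6 to 37 days over across the windows, once for each affected subject still on drug after Week 36.

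This rests on two assumptions: the column alignment in Step 1, which two independent rows support, and reading 3 months as 89 to 92 days. How many core-antibody-positive subjects would be enrolled is not stated, so the number exposed to the gap cannot be estimated. The issue is confined to safety monitoring; sample size and efficacy analyses are unaffected.

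**What to change.** Add a viral monitoring mark at Week 44 in Appendix 2. This removes the only post-baseline gap that is nominally over 3 months. It leaves the Screening-to-Week 12 interval and the 94-day window edge of Weeks 24 to 36 as they are.

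Rewording criterion 20 to name the four scheduled weeks would also end the contradiction, but it would keep the 112-day gap, so the added test is preferable.

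The cost is a protocol modification with IRB/IEC approval (Section 9.2.1) and one HBV DNA assay per core-antibody-positive subject at a visit where blood is already drawn. Whether an extra tube is needed is not stated; sample handling is in a separate laboratory manual.
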